## **Data Collection**

All admitted SCI patients will be evaluated by the research supervisor in the setting for eligibility within three days of admission to the inpatient rehabilitation setting, until the desired sample size is reached. Eligible individuals will sign a consent form and then be assigned randomly to one arm of the study by the research supervisor. The allocation sequence will be concealed from patients, therapist and, assessor. The data about exposure to the educational intervention will be collected by a separate research assistant by phone and will be concealed

from the assessor. Each occupational therapy department will assign four therapists to follow up the trial cases – two for the intervention and two for control group. All the staff in the occupational therapy department, participants, and assessors will be requested not to discuss the trial and intervention material between them. The importance of concealing any information until the end of the study will be explained. Study participants are not allowed to switch between occupational therapists or study arms. They will be asked not to participate in other educational interventions (peer or external) related to their rehabilitation or seek treatment outside their trial. The head of occupational therapy department within each rehabilitation setting will supervise participants and assigned occupational therapists in both study arms to reduce contamination bias such as sharing intervention content with the control group, sharing similar time and space of occupational therapy sessions, and exchange of therapists.

Contamination bias due to already existing background and/or receipt of additional educational interventions will be measured within each arm of the study (Chi-Square test to compare the progress means). However, no case will be eliminated from statistical analysis due to contamination bias.

The study will adopt approaches to prevent loss of participants to follow-up by making questionnaires as easy to complete as possible, providing incentives in the form of a free copy of the educational manual for the control group, and explaining the importance of the study (Magill, et al., 2019).

The researchers will use the same outcome measures all through the study and with both of study arms. Biographical data will be collected by a research assistant once on the participant's admission and consent to participate. ADL data collection from each participant in the study will take place in a face-to-face interview twice (on admission before providing with the educational manual and 6 weeks later) using: (a) Patient-administered SCIM-SR and (b) Research assistant-administered SCIM-III, the Private Religiousness Practices Scale, Organizational Religiousness Short-Form, and the domains of ADL covered by the educational manual including driving and community mobility, personal device care, health management and maintenance, Wudu, and Salat. The data will be used to compare the results and means of both groups, answer the research question, and test the study hypothesis.

Polit, et al. (2001) pointed out that the validity of the experimental study can be threatened by history, selection, and maturation. This study finding's validity will be enhanced by concealing intervention group using a blinded assessor. The bias of sampling and contamination will be

minimized through randomization and assuring freedom of participation and anonymity of participants.

Objective data collected in clinical settings using valid and reliable tools is essential for evaluating the impact of an intervention (Polit, et al., 2001). The validity and reliability of the data collected and results of the study will be improved using standardized measurement tools such as SCIM-III and SCIM-SR.

**Biographical Data Collection Tool:** an English 24-item tool that captures demographic and socioeconomic data including age, gender, marital status, level of education, employment, monthly income, accommodation, diagnosis, and cause and type of SCI. The researchers developed the tool to be used in English version in this study.

**Spinal Cord Independence Measure-Self Reported (SCIM-SR):** a patient-reported 17-item tool that evaluates the ability of a person with SCI to perform specified activities independently, with assistance, or with assistive devices. The tool uses an ordinal scale.

Research supports the criterion validity of SCIM-SR as compared with SCIM III. Pearson correlation and ICC coefficients of the total and the subscale scores met the quality criterion of being above 0.7. The tool is not available in Arabic (Fekete, et al., 2013). The first author will translate the SCIM-SR to Arabic. The Arabic translation will be piloted in the pilot study.

**Spinal Cord Independence Measure-III (SCIM-III):** a 17-task tool that evaluates the ability of a person with SCI to perform specified activities independently, with assistance, or with assistive devices. It is therapist-reported and requires 30 to 45 minutes to complete by assessment but, the interview requires less time [about 20 minutes] (Fekete, et al., 2013). The SCIM has been evaluated in multiple countries including the Middle East and it appears to be resistant to cross-cultural differences. The SCIM-III is valid for use in clinical practice to evaluate function and plan goals of rehabilitation (Glass, et al., 2009). The tool uses an ordinal scale with total score range between 0-100. A higher score indicates greater ADL performance. The SCIM-III has good reliability: Cronbach's alpha: 0.70-0.78, Kappa co-

efficient: 0.64-0.84. Pearson correlation and ICC coefficients of the total and the subscale scores met the quality criterion of being 0.84-0.94. The tool is not available in Arabic and will be used in its English version (Anderson, et al., 2008). Good English language comprehension, and the ability to read and write is mandatory for therapists.

**The Private Religious Practices Scale:** a 4-item tool that measures the frequency of individual's involvement in religious behaviours: prayer, religious attendance (attending a church or mosque), reading the Bible/Quran, and watching religious programs on television (Fetzer Institute, 2003). The tool uses an ordinal scale and it has acceptable reliability ( $\alpha=0.70$ ). It can be therapist-reported or patient-reported. The tool is not available in Arabic and will be used in its English version (Bodling, et al., 2013).

**Organizational Religiousness Short-Form:** a 2-item tool that measures the involvement of the individual with a formal public religious institution such as a church or mosque (Fetzer Institute, 2003). The tool uses an ordinal scale and has accepted reliability ( $\alpha=0.70-0.76$ ). It can be therapist-reported or patient-reported. The tool is not available in Arabic and will be used in its English version (Bodling, et al., 2013).

**SADL-eM adherence therapist-report questionnaire:** Based on the Morisky Medication Adherence Scale [MMAS] (De las Cuevas and Penate, 2015), this tool measures any change to the supplied SADL-eM in terms of content of the intervention, topics, techniques described, mode, format, and degree of individualization of the intervention. The tool keeps record of educational sessions by day, duration, intensity, and elements covered. This tool was developed by the researchers and will be used in its English version.

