The purpose of the SADL-eM is to serve as a treatment tool during inpatient rehabilitation. Over the first week of admission of each person with SCI in each facility, a research clinical supervisor will recruit study participants based on the study eligibility criteria, obtain consent, and assign each consenting patient to one of the two study groups. They will then provide each participant in the intervention group with a SADL-eM hard copy, and explain the purpose of the manual and how to use it. The manual will be reviewed by the treating occupational therapist and the person with SCI during their treatment sessions. During occupational therapy sessions, the therapist will refer to the relevant chapter of the manual. The therapist will also indicate to the participants which parts of the manual are not relevant to them (based on their gender, driving status, or level of SCI). Participants' queries on the content of the manual will be answered by the treating occupational therapist. The therapist will include the manual in as many SADL-eM educational sessions as required, but not less than three sessions per week with 15 minutes per session. The minimum level of clinical experience of each treating occupational therapist will be two years. Good Arabic language comprehension, and the ability to read and write is mandatory for both therapists and patients. No other special skills or experience are required.

The participants will keep the manual to review after sessions and after discharge from the inpatient rehabilitation setting. For the purposes of the study, blinding and bias reduction, the therapists and the participants in the intervention group must not share any part of the manual or information included with other patients or staff. The research assistant who performs data collection, the clinical supervisor, and occupational therapy team will be invited for informational session prior to data collection in each of the participating settings. The informational session will focus on the study purpose, recruitment, eligibility criteria, use of

the SADL-eM, roles, bias reduction, and blinding. Use of data collection tools will take place in a separate session with the research assistant. The principal researcher will answer all questions of the research team during informational sessions and during the research.

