### **Trial status**

Recruitment is expected to start by March 2021 and is due to continue until the February 2022. The pilot study will start in January 2020.

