### 46 Random Numbers

43 13 12 81 57 53 75 09 68 07 74 35 14 90 31 25 66 56 59 80 86 20 58 60 77 03 85 45  
73 50 84 55 19 36 33 42 16 70 01 91 28 34 39 24 69 04

**Specs:** This table of 46 random numbers was produced according to the following specifications: Numbers were randomly selected from within the range of 1 to 92. Duplicate numbers were not allowed. This table was generated on 8/19/2020.

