**Figure 1: Random generated numbers of intervention group**

## **Box 1: inclusion and exclusion criteria**

Inclusion criteria
▪ Confirmed SCI diagnosis by computed tomography or magnetic resonance report.
▪ ASIA: A, B, and C
▪ Age between 18 and 65 years old.
▪ Stable medical condition.
▪ Time elapsed after SCI is not more than 6 months.
▪ Minimum time of stay in inpatient rehabilitation unit is six weeks.
▪ Active involvement in rehabilitation program.
▪ Sufficient comprehension (read/write) of the Arabic language.
Exclusion criteria
▪ Unconfirmed diagnosis.
▪ Patients who have communication and/or cognitive disorders such as global aphasia and memory deficit.
▪ Patients with disturbed level of awareness such as coma or lethargy.
▪ Time elapsed since SCI is more than 6 months.
▪ ASIA: D and E
▪ Unstable medical condition.
▪ Patients who have other cause(s) of disability in addition to SCI such as stroke or amputation.
▪ Age less than 18 or more than 65 years old.
▪ Time of stay in inpatient rehabilitation unit is less than six weeks.
▪ Inactive involvement in rehabilitation program.
▪ Patients with a progressive disease or a psychiatric condition that would interfere with active participation in rehabilitation program.
▪ Patients with cardiovascular contraindications.
▪ Persons who become walking ambulatory during the inpatient period.
▪ Persons with complete tetraplegia C4 or above.
▪ Persons on mechanical ventilator.

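### The supervisor who screens, consents and assigns patients is not covered by allocation concealment, no concealment mechanism is described, and the intervention-group numbers are printed in the protocol

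*Combined protocol and SAP*

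**What the plan says.** Two sections describe entry and allocation, and both give them to one role. In the section on the SADL-eM, "a research clinical supervisor will recruit study participants based on the study eligibility criteria, obtain consent, and assign each consenting patient" to a study group, and the text continues: "They will then provide each participant in the intervention group with a SADL-eM hard copy". Data Collection has the research supervisor evaluate all admitted SCI patients within three days of admission, and adds: "Eligible individuals will sign a consent form and then be assigned randomly to one arm of the study by the research supervisor".

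The only statement about concealing the sequence follows directly: "The allocation sequence will be concealed from patients, therapist and, assessor". The supervisor is not named there. The section on participants and sample size calls the method simple randomization and fixes 45 patients per arm. It gives no procedure for holding or releasing assignments.

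Near the end of the document is a table of 46 random numbers drawn from 1 to 92. It is captioned "Random generated numbers of intervention group" and carries the note "This table was generated on 8/19/2020". Trial status says: "Recruitment is expected to start by March 2021".

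**The concern.** Concealment has to cover the person who decides whether a patient enters. If that person can foresee the next arm, a borderline patient can be admitted, delayed or turned away according to the arm that is due. Randomization then no longer guarantees comparable groups.

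Box 1 leaves room for this. Many of its criteria are objective (age, ASIA grade, time since injury). Stable medical condition and "Active involvement in rehabilitation program" are judgements, made within three days of admission by the same role that assigns.

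The planned analysis does not remove the problem. A stable baseline difference cancels from the group-by-time effect in a pre/post comparison, but steering related to expected change does not. Involvement in rehabilitation is plausibly related to gain in ADL. Assessor blinding acts on measurement after entry, and intention-to-treat keeps patients in their assigned arm; neither repairs selection at entry. The statement under Data Collection that randomization minimises sampling bias depends on this step.

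**Working it through.** **1. Roles against concealment.**

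| Role | Function | Sequence concealed from this role? |
|---|---|---|
| Patient | Participant | Yes, stated |
| Therapist | Delivers care | Yes, stated |
| Assessor | Measures outcome | Yes, stated |
| Research (clinical) supervisor | Screens, consents, assigns, hands out the manual | Not stated |

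The two sections use slightly different titles for the supervisor. The duties coincide, so one role is the natural reading.

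**2. Mechanism.** The available text contains three related items, and none of them is a mechanism: the words simple randomization, assessor blinding (described under Data Collection as concealing the intervention group), and an information session on bias reduction and blinding.

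**3. The printed list.** A count gives 46 distinct numbers, which matches its own specification. Of these, 45 lie within 1–90 and one (91) lies outside. For 90 patients it therefore gives 45 intervention and 90 − 45 = 45 control, so it fixes the arm of every number from 1 to 90. For example, 55–60 are all intervention and 61–65 all control. The list's length is not part of the concern.

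**4. Timing.** From 19 August 2020 to 1 March 2021, the earliest day of the stated start month, is 12 + 30 + 31 + 30 + 31 + 31 + 28 + 1 = 194 days.

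**5. How predictable assignments could be.**

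- *List readable.* Assume the printed numbers are trial-wide enrolment order and the recruiter has the protocol and the running count. Then up to 90 of 90 assignments are known in advance.
- *List hidden, 45:45, unblocked, all past assignments seen.* The best guess is the arm used less so far, and a tie is a coin toss. Expected correct guesses = 45 + (2^90 / C(90,45) − 1)/2. Since 2^90 / C(90,45) = 11.92, this is 45 + 10.92/2 = 45 + 5.46 = 50.46 of 90, or 56.1%. Simulation of 8,000 lists also gave 56.1%.
- *Same hidden list, only one hospital's past assignments seen.* With an assumed 30 of the 90 patients, simulation gives 51.7%.
- *Chance.* 50%.

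The 56% and 52% figures describe the position once the list is hidden. They are the benchmark for the fix, not a measure of the present weakness.

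**The case against.** The strongest reply is that the printed list may not be the operative sequence. It sits directly below a flow-diagram title marked as a dummy and shares its figure number. It covers 92 numbers when 90 patients are planned, and nothing says who will use it or in what order. Recruitment also appears to run hospital by hospital, with no described sharing of a trial-wide count. A recruiter who knew only a local count and simply scaled it to the printed list would do no better than about 50%, assuming patients arrive equally and at random across the three hospitals. One who matched past local assignments to the list could do better. On this view 90 of 90 is a worst case. In addition, all admissions are screened and many criteria are objective.

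Most of this is fair as a limit on size. The 90 of 90 figure is conditional and should be read that way. However, the dummy marking attaches to the flow diagram, while the list has its own caption identifying it as the intervention group's numbers. Even if the list is set aside entirely, the recruiter is still outside the concealment statement and no mechanism is described.

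A second objection is that literal simple randomization, with independent assignments, would make past assignments uninformative, so that 56% overstates what could be guessed. That is correct for independent assignments. The stated arms of 45 and 45 imply a fixed-total list, which is the case computed here. Neither version protects against a recruiter who can see the sequence.

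Finally, the flow diagram is not shown and some pages were not available, so the absence of a mechanism is a statement about the visible text.

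**Conclusion.** The concern holds and should be fixed before enrolment begins. Followed as written, the plan lets the person who makes the eligibility judgements also make the assignment, with nothing stated to stop that person foreseeing it. What is established is missing protection. The documents do not say that the supervisor holds the list, or how its numbers map to patients.

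The resulting bias cannot be sized from the documents. Foreseeable assignments could reach 90 of 90 under the assumptions above, compared with about 50 of 90 under a hidden, unblocked 45:45 list. Confidence is high on the omission and the missing mechanism; the worst-case figure is only as good as its assumptions. Selection at entry cannot be undone by analysis afterwards.

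**What to change.** - Discard the printed list. Generate a new 45:45 list for 90 patients and keep it out of the protocol.
- Name an existing researcher who does not recruit to hold it. Alternatively, use sequentially numbered opaque sealed envelopes and state who prepares them, which should not be the recruiter.
- Release each assignment only after eligibility, consent and baseline SCIM-SR and SCIM-III are recorded. The current text places baseline before the manual is given, but does not place it before assignment.
- Add the recruiting supervisor to the roles in Data Collection from whom the sequence is concealed until each assignment.
- Keep the list unblocked. The supervisor hands out the manuals and so sees past assignments; a hidden unblocked list stays hard to guess even so. Blocking or stratification by hospital is not part of this change.

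The cost is one new list, envelopes or a call to an existing researcher, a few lines of protocol text, and a slight delay at each enrolment. The sample size and staffing are unchanged. The change must be made before the first patient is enrolled.

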#### **Participants, sampling method, sample size, and setting**

Participants in the study will be SCI inpatients from the Gaza Strip, both genders, of any cause or type of SCI, and age 18-65 years. They will be recruited from admitted inpatients in one of the three rehabilitation settings (Hamad, ElWafa, or ElAmal Rehabilitation hospitals). Readmissions will be included in the study if they are eligible. These three inpatient rehabilitation hospitals are located in the Gaza Strip of Palestine and are private sector health services. They provide comprehensive rehabilitation services. Their rehabilitation teams include physical rehabilitation doctors, rehabilitation nurses, physiotherapists, occupational

therapists, speech therapists, clinical dietitians, psychologists, social workers, orthoptists, and community-based rehabilitation workers. The sample size was determined to detect an effect size of 15%, power of 80%, 5% margin of error, and 95% Confidence Interval (CI). The study sample of 90 SCI individuals will be randomized to two groups, conventional therapy (n1=45) and intervention/SADL-eM & conventional therapy (n2=45) using a simple randomization approach. Inclusion and exclusion criteria are listed in Box 1.

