For the purposes of the current study, the SADL-eM will be provided during face-to-face individual occupational therapy sessions without any constraints regarding treatment area. It could be occupational therapy department, patient ward, and educational activities room. The face-to-face manual delivery does not require any infrastructure or special equipment.

The number of sessions, time allocated, and frequency are determined by each therapist and participant. Determinants may include participant's capabilities, potentials, and progress during treatment; and the scope of the service such as time allocated for each patient, therapist-patient ratio, and frequency of inpatient sessions. The therapist and the participant will continue to use the manual during treatment sessions until they decide there is no need for further use of the manual or the participant is discharged. Treating occupational therapists will retain records of any change or modification of the SADL-eM administration. The researchers will conduct a pilot study in a similar sample of 15 S people with SaCIs to improve the use of intervention and data collection tools.

Nonadherence to medical treatment in clinical trials of medical efficacy has serious consequences on the quality of research. It may obscure data collected and disrupt findings obtained (Quittner, et al., 2000). The steps to ensure adherence to the intervention during study include clearly defining the intervention, measuring, and then comprehensively reporting adherence to the intervention. Attendance records collected by the therapist (times, duration, and intensity of treatment; manual elements covered) and SADL-eM adherence therapist-report questionnaire will be used to measure and report adherence to the SADL-eM intervention. The manual will be made freely available on the Stellenbosch University website when the research is complete.

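### About six therapists per arm treat only that arm, but the SCIM-SR analysis names no therapist term; if therapists within a hospital differ, its 95% interval is too narrow

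*Combined protocol and SAP*

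**What the plan says.** The Participants section names three hospitals and randomizes 90 individual patients, 45 to each arm, "using a simple randomization approach". Its power sentence gives 80% power for a 15% effect on an undefined scale, with no allowance for clustering.

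Data Collection sets the staffing: "Each occupational therapy department will assign four therapists to follow up the trial cases", split as "two for the intervention and two for control group". It adds: "Study participants are not allowed to switch between occupational therapists or study arms". It does not say how the two pairs of therapists are chosen, or how patients are shared between the two therapists of an arm.

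On delivery, the manual section says: "The number of sessions, time allocated, and frequency are determined by each therapist and participant". In Data Collection, the adherence questionnaire is described thus: "this tool measures any change to the supplied SADL-eM in terms of content of the intervention, topics, techniques described, mode, format". The manual section also sets limits on variation: "not less than three sessions per week with 15 minutes per session", and "The minimum level of clinical experience of each treating occupational therapist will be two years". Staff attend an information session first.

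The Abstract names repeated measures ANOVA for the effect. Data Analysis names repeated measures ANOVA and linear mixed models to compare the groups. It mentions random effects only as a general merit of mixed models and specifies no therapist or hospital term.

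**The concern.** Patients are randomized individually, but each therapist belongs to one arm. Any difference between therapists in the same hospital therefore enters the comparison of arms. An analysis that treats 45 patients per arm as independent does not count it, so the standard error is too small. A chance difference between two sets of about six therapists can then pass as an effect of the manual more often than 1 time in 20.

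Bias is a separate risk from the same staffing rule. If a department gave its stronger pair to one arm, no model term could separate their skill from the manual.

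**Working it through.** **Inputs from the documents.** 3 hospitals × 2 therapists per arm = 6 therapists per arm, 12 in all. 45 / 6 = 7.5 patients per therapist on average.

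**Assumed.** The therapist share ρ of the variance of SCIM-SR change within a hospital: 0 / 0.02 / 0.05 / 0.10. The documents give no value.

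**The plan's own figure.** Read 15% as f = 0.15 for the group-by-time interaction, with an assumed pre/post correlation of 0.5. Then λ = f² × N × 2 / (1 − 0.5) = 0.0225 × 90 × 2 / 0.5 = 8.1, and power on 1 and 88 df is 0.804. In terms of change, λ = N d² / 4, so 8.1 = 90 d² / 4 and d = 0.6 SD. This reading is not unique: correlations of 0.3 and 0.7 give N = 126 and 56, and a 15-point difference with an assumed SD of 25 gives 44 per arm. All of these treat patients as independent.

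**Size of the effect.** The variance of the arm difference is multiplied by

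- V = 1 + (7.5 − 1)ρ if therapists in both arms differ;
- V = 1 + (7.5 − 1)ρ / 2 if only intervention-arm therapists differ.

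The unclustered test then errs with probability of about 2[1 − Φ(1.96 / √V)]. The simulations used 40,000 null trials with arms balanced in each hospital, caseloads of 7 to 8 and no hospital variance.

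| ρ | V, both arms | Formula | Simulated | V, intervention arm only | Formula | Simulated |
|---|---|---|---|---|---|---|
| 0 | 1.000 | 5.0% | 5.1% | 1.000 | 5.0% | 5.2% |
| 0.02 | 1.130 | 6.5% | 6.5% | 1.065 | 5.8% | 5.8% |
| 0.05 | 1.325 | 8.9% | 9.0% | 1.1625 | 6.9% | 7.0% |
| 0.10 | 1.650 | 12.7% | 13.0% | 1.325 | 8.9% | 9.0% |

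With randomization not stratified by hospital, and therapists in both arms differing, simulated coverage of the nominal 95% interval was 95.1% at ρ = 0, 90.4% at 0.05 and 86.4% at 0.10. Uneven caseloads (assumed 14/3, 10/4 and 8/6 per arm and hospital) raise the both-arms error to 7.0 / 10.1 / 15.1% at ρ = 0.02 / 0.05 / 0.10.

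**Hospitals.** With no therapist variance and hospital shares of 0.05 / 0.10 / 0.20, the error is 4.6 / 4.3 / 3.7%, so there is no inflation. Adding hospital without therapist does not cure the problem: at hospital share 0.10 and ρ = 0.05 / 0.10 in both arms, the error is 9.6 / 14.1%.

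**Remedies.**

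- Therapist means with hospital fixed, on 12 − 3 − 1 = 8 df: about 5% in every case tested.
- REML model with baseline, hospital fixed and therapist random: 2.9–5.2% if 8 df is used except when the therapist variance is estimated as zero, but about 1.6–3.8% if 8 df is kept throughout. The variance was estimated as zero in 55–56% of trials at ρ = 0 and 40–50% at 0.02, so this rule matters.
- The same REML model without hospital, at hospital share 0.10: 1.5–2.8%, too conservative.

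**Price.** At ρ = 0 the interval on 8 df is wider by 2.306 / 1.987 = 1.16. Power of the therapist-means analysis at 0.6 SD uses noncentrality 0.6 / √(2V / 45) on 8 df:

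- ρ = 0: noncentrality 2.846, power 70%.
- Both arms, ρ = 0.02 / 0.05 / 0.10: noncentrality 2.677 / 2.472 / 2.216, power 65 / 58 / 50%.
- Intervention arm only: noncentrality 2.758 / 2.640 / 2.472, power 68 / 64 / 58%. Simulations gave 67–68 / 63–65 / 58–60%.

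**The case against.** Four objections carry weight.

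**The driver is assumed.** No intraclass correlation is documented. The session floor, the experience requirement and the information session limit variation. The occupational therapist is one member of a large rehabilitation team, the clinical supervisor hands over and explains the manual, and patients keep it to read alone. The share may be small; at 0.02 in the intervention arm only, the excess is about one point or less. This stands, and it is why the conclusion is conditional.

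**The textual evidence concerns delivery of the manual.** A reader might infer that the freedom over sessions, and the recording of changes to the manual, show an inflated type I error. They do not. If the manual does nothing, different amounts of it create no differences between therapists. The intervention-arm-only figures describe interval coverage when the manual's effect varies by therapist. Inflation under a true no-effect null needs differences in general skill, which would be expected in both arms and which the documents neither show nor exclude.

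**The remedy costs power.** This stands. The fall from 80% to 70% is the mildest case, with no therapist variance at all.

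**The plan already lists mixed models.** They could carry a therapist term, so this is a gap in specification and not a wrong method. That is fair, but following Data Analysis as written would allow a model without the term.

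**Conclusion.** The concern holds in conditional form. About six therapists per arm, each confined to one arm, follows from the text, as does the absence of a therapist term and of a clustering allowance. If therapists within a hospital differ in their patients' SCIM-SR change, the planned interval is too narrow: negligibly at a share near zero, materially at 0.05 to 0.10 (type I error about 9 to 13% if both arms differ; non-coverage about 7 to 9% if only the intervention arm does).

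The documents do not support three stronger readings. They do not show that the interval is in fact too narrow, because the share is unknown. They do not make hospital differences the cause, because both arms are present in each hospital. They do not show that therapists were chosen to favour an arm; they only leave the choice unstated.

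The error rates rest on the assumed shares. The power figures also rest on reading 15% as 0.6 SD of change.

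**What to change.** 1. Before recruitment, draw lots in each department for which two therapists serve which arm. Any difference between the pairs is then due to chance, which the analysis can count, and not to choice, which it cannot.
2. Record the treating therapist for every patient in both arms. The attendance records described in the manual section serve adherence to the manual, and no section says that control patients' therapists are recorded.
3. Pre-specify a SCIM-SR analysis with hospital as a fixed effect and therapist, nested in hospital and arm, as a random effect. State the degrees-of-freedom rule, including what is done when the therapist variance is estimated as zero. Therapist means with hospital on 8 df are a simpler alternative. Report the therapist-adjusted interval at least beside the planned one, and claim no effect of the manual from the unclustered interval alone.
4. Say in the Participants section that 80% power assumes independent patients.

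The cost is a draw at three sites, one data field, two model terms and one sentence. No extra patients are needed if the lower power shown above is accepted and stated; keeping 80% would need more. On the design effect alone, with therapists in both arms differing, N would be 90 × 1.325 ≈ 120 at share 0.05 and 90 × 1.65 ≈ 149 at 0.10, before the loss from 8 df. If recruitment has begun, step 1 is no longer possible, but steps 2 to 4 are.
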